7 ASSESSMENT OF SAFETY

7.1 ADVERSE EVENT (AE) AND SERIOUS ADVERSE EVENT (SAE) REPORTING

The main investigator at each of the participating institutions will be responsible daily for the appropriate implementation of study protocols and for patient safety. All adverse events will be reported to the DSMB, to the local IRB of the participating institution where the adverse event occurred per their respective reporting guidelines, and if required, to the NHLBI. Each adverse event will be classified by the site investigator as ‘study-related’ or ‘not study related’ and reviewed by the DSMB for adjudication. Serious adverse events (death, procedural complications, or hospitalizations for any reason) will be reported to the coordinating center and the local IRB (per their reporting guidelines) within 48 hours of adverse event awareness.

7.2 REPORTING PROCEDURES

The study clinician will have oversight of completed SAE Forms. Reporting of the forms should occur within the following timelines:

- All deaths and immediately life-threatening events, whether related or unrelated to the clinical trial, will be recorded on the SAE Form and submitted to the study sponsor within 48 hours of site awareness.
- Other SAEs regardless of relationship will be submitted to the study sponsor within 72 hours of site awareness.

All SAEs will be followed until resolution or until the site investigator deems the event to be chronic or stable. Other supporting documentation of the event may be requested by the study sponsor and should be provided as soon as possible.

7.3 SAFETY OVERSIGHT

Safety oversight will be under the direction of a DSMB composed of individuals with the appropriate expertise, including cardiologists. The DSMB will meet at least quarterly to assess safety and efficacy data on each arm of the study. The DSMB will operate under the rules of an approved charter that will be written and reviewed at the organizational meeting of the DSMB. At this time, each data element that the DSMB needs to assess will be clearly defined. The DSMB will provide its input to the NHLBI.

8 CLINICAL MONITORING

The primary responsibility of the DSMB, an independent group of experts that advises the study investigators, is to oversee the progress of the study and review adverse events. All adverse events in both arms of the clinical trial will be reviewed and adjudicated as ‘research-related’ or not. Stoppage rules of the clinical trial will be mandated by the DSMB if examination of the adverse events revealed that one treatment arm is clearly superior to the other treatment for the primary endpoint of all-cause mortality. The DSMB will also review the overall progress of the trial, the quality of data collection, the safety and confidentiality of data storage, and the overall management of the trial. A Data and Safety Monitoring report will be generated including information on study status and enrollment milestones, quality of data collected, and safety data.

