- Précis:** Pilot trial designed with a two part aim at enrollment. Aim 1 is designed as a randomized, controlled trial for older patients (≥ 75 years) who are indicated for CRT device implantation to receive a CRT-P or CRT-D. Information collected will help to assess the ability to enroll and retain older patients in a randomized controlled trial of CRT-P versus CRT-D in preparation for a large pivotal trial. Aim 2 is a non-randomized, observational study of patients who were offered inclusion into Aim 1 but refused to participate. Aim 2 subjects present an opportunity to understand the reasons why older patients may refuse enrollment into a randomized trial as well as still allowing for collection of data regarding their chosen CRT device.
- Objectives:** **Primary Objective:** Feasibility of enrolling and maintaining elderly heart failure patient in CRT-P vs CRT-D randomized trial.
Secondary Objectives: Examine predictors of refusing randomization and of choosing CRT-P vs. CRT-D device implantation in elderly patients.
- Endpoint** **Primary Endpoint:** The ability to enroll in the randomized controlled trial of CRT-P versus CRT-D patients.
Secondary Endpoints: Determinants of refusing participation in CRT-P versus CRT-D clinical trial.
- Population:** Patients 75 years or older who are clinically indicated for CRT device implantation based on published guidelines⁶ will be considered for this trial. The racial, gender, and ethnic characteristics of the proposed subject population represent the populations cared for at the participating institutions. Subjects meeting all inclusion and none of the exclusion criteria for Aims 1 and 2 will be enrolled in this research. No exclusion criteria shall be based on race, gender, or HIV status. Patients younger than 75 years of age are excluded based on study rationale and design.
- Study Type:** Pilot trial with two clinical Aims. Aim 1 is a randomized clinical trial and Aim 2 is an Observational clinical trial.
- Number of Sites**
Enrolling Participants: Total of four participating sites
- Study Duration:** Approximately 24 months
- Participant Duration:** Up to 18 months from enrollment

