3 OBJECTIVES AND PURPOSE

[figure not shown]
The primary objective is to evaluate and determine the feasibility of enrolling and maintaining elderly heart failure patients in the CRT-P versus CRT-D randomized trial. Additionally, for Aim 2, the observational arm will also maintain the same objective. Secondary objective is to examine the predictors of undergoing Pacemaker versus Defibrillator device implantation in elderly patients (≥ 75 years).

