4 STUDY DESIGN AND ENDPOINTS

4.1 DESCRIPTION OF THE STUDY DESIGN

The design of this pilot study is in two parts corresponding to Aims 1 and 2 (Figure 1). Aim 1 is designed as a pilot randomized, controlled trial to be conducted at 4 institutions in the United States. It will randomize older patients (≥ 75 years) who are indicated for CRT device implantation to receive a CRT-P or a CRT-D. The choice of the design of Aim 1 was intended to mimic the design of a future large, multicenter, non-inferiority trial which would provide definitive answers regarding the relative impact of CRT-P versus CRT-D on total mortality and QOL in older patients. This specific design is necessary to allow the gathering of hard data on rates of screening of patients, acceptance of enrollment, randomization, device implantation, and patient retention during follow-up. Any design variations are likely to introduce biases which would increase the chances of flawed design of the pivotal trial.

Aim 2 is a non-randomized, observational study of patients who were offered inclusion into Aim 1 but refused to participate. We speculate that a majority of those patients who refuse participation in the randomized pilot trial do so because of a strong preference for CRT-P or CRT-D. This cohort complements Aim 1 and presents an opportunity to understand the reasons why older patients may refuse enrollment into a randomized trial of CRT-P versus CRT-D and to examine the demographic and clinical determinants associated with choosing a CRT-P versus a CRT-D device. It also provides the means to measure patients' QOL and satisfaction³²⁻³⁴ with decision (CRT-P or CRT-D), at baseline and 6 months after enrollment into this observational cohort.

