4.2 STUDY ENDPOINTS

4.2.1 PRIMARY ENDPOINT

With the Aim 1 randomized subjects the primary endpoint is the ability to enroll in the randomized controlled trial of CRT-P versus CRT-D patients. The subjects enrolled with aid in determining and assessing feasibility of screening, enrolling, randomizing, and retaining participants in this pilot trial.

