4.2.2 SECONDARY ENDPOINTS

The subjects enrolled in Aim 2 will help to determine the clinical and demographic characteristics of subjects who refused participation in the pilot randomized trial and to compare them to those in Aim 1. Therefore the secondary endpoint is the determination of predictors of refusing participation in CRT-P versus CRT-D clinical trial.

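### Does the stoppage sentence need changing because it calls all-cause mortality the primary endpoint when the pilot's primary endpoint is ability to enroll?

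*Combined protocol and SAP*

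**What the plan says.** The stopping provision is one sentence in section 8. It opens "Stoppage rules of the clinical trial will be mandated by the DSMB if examination of the adverse events revealed", and the trigger in full is that "examination of the adverse events revealed that one treatment arm is clearly superior to the other treatment for the primary endpoint of all-cause mortality".

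The endpoint definitions differ from this and agree with each other:

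- The Précis gives the primary endpoint as "The ability to enroll in the randomized controlled trial of CRT-P versus CRT-D patients". Section 4.2.1 repeats it.
- Section 3 states: "The primary objective is to evaluate and determine the feasibility of enrolling and maintaining elderly heart failure patients".
- Section 4.2.2 states: "the secondary endpoint is the determination of predictors of refusing participation in CRT-P versus CRT-D clinical trial".
- Section 4.1 leaves the mortality comparison to a later, large non-inferiority trial, "which would provide definitive answers regarding the relative impact of CRT-P versus CRT-D on total mortality and QOL".
- Section 9.1 reports mortality by arm descriptively. Section 9.2 sizes Aim 1 on the precision of a retention proportion.

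Section 7.3 has the DSMB review both safety and efficacy by arm at least every quarter, under a charter that is written and reviewed at its organizational meeting. That charter is not among the documents.

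**The concern.** The sentence is the only outcome-based stopping provision in the protocol. Section 5.6 adds only a general clause on suspension for reasonable cause. If that one sentence misnames the primary endpoint, a reader may ask whether the DSMB is meant to monitor mortality, feasibility or both. A reader may also ask whether the pilot has an undeclared efficacy endpoint for which it is neither sized nor analysed.

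A second worry concerns timing. Read literally, the rules are set only once the data have shown superiority, that is, after the DSMB has seen results by arm. With 50 patients there would be few deaths, and an uneven split could arise by chance. A pilot stopped on such a split would lose the enrolment and retention information it was set up to collect.

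**Working it through.** **1. What the trial is sized for.** Section 9.2 supposes 40 of 50 patients retained:

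0.80 ± 1.96 × √(0.80 × 0.20 / 50) = 0.80 ± 1.96 × 0.0566 = 0.689 to 0.911.

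This reproduces the printed 68.9% to 91.1%. The largest standard error is √(0.25/50) = 7.07%, printed as 7%. The largest margin is 1.96 × 7.07% = 13.9%, which the plan prints as 13%; that does not bear on this point. Mortality does not enter the sizing.

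**2. Mortality across the sections.**

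| Place | Role of all-cause mortality |
|---|---|
| Précis; 3; 4.2.1; 4.2.2 | Neither primary nor secondary |
| 2.2 | Part of the rationale (whether CRT-P is equivalent to CRT-D on mortality and QOL) |
| 4.1 | Question for the future trial |
| 6 | Collected as a clinical event and adjudicated |
| 8 | Called primary, in the stopping sentence only |
| 9.1 | n (%) by arm, no test |
| 9.2 | Not used |

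Section 8 is the only place that gives mortality primary status.

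**3. Can the sentence be misapplied?** Put the real primary endpoint into it: adverse-event review would have to show one arm superior on ability to enroll. Under section 5.4, patients consent and are then randomized, so enrolment is complete before an arm exists. Retention, which is part of the primary objective, could differ by arm, but adverse-event review would not reveal that, and the sentence does not mention it. The only workable reading is the one printed, all-cause mortality.

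**4. What removing the label would change.** Outcome watched: all-cause mortality, before and after. Trigger: one arm clearly better, before and after. Decision-maker: the DSMB, before and after. Sample size, analyses in 9.1 and reported results: unchanged.

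**5. How much mortality information there would be (illustration).** The plan gives no mortality rate, allocation ratio, test or level. Assume 25 per arm, equal mortality in both arms, even accrual over the 15 months of section 9.3, 24 months in total and follow-up to closure. Let λ = −ln(1 − annual rate)/12. Expected deaths in both arms together are

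50 × {1 − [exp(−9λ) − exp(−24λ)] / (15λ)}.

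At 10% per year, λ = 0.00878, and the result is 50 × [1 − (0.924 − 0.810)/0.1317] = 6.7. Rates of 5% to 25% give 3.4 to 16.1. With the Précis limit on participation, "Up to 18 months from enrollment", they give 3.2 to 15.3.

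At a single look, a split of 0 against 6 has two-sided Fisher p = 2 × C(25,6)/C(50,6) = 2 × 177,100/15,890,700 = 0.022. Power for 10% against 20% mortality is about 9%.

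These figures show that the pilot cannot settle a mortality comparison, which section 4.1 already leaves to the later trial. They do not measure the mislabelling, which is the same at any death rate.

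**The case for a change.** The strongest case for a change is that a stopping provision should be exact, that the charter's authors will work from the protocol, and that the correction costs a few words. Section 7.3 adds to the doubt by mentioning efficacy review in a pilot with no listed efficacy endpoint. The inconsistency is real and is not explained by redaction or by an amendment log. That much stands.

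The consequences do not follow. A charter based on section 8 would monitor mortality. One based on the endpoint sections would find no between-arm criterion there and would have to return to section 8.

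The timing worry depends on a literal reading of an awkward sentence, which can equally mean that stopping will be mandated if superiority is seen. An organizational meeting at which the charter is written would ordinarily come before any review by arm. What counts as clear superiority over repeated looks is a fair matter for that charter, and its absence from the public documents does not show that it was left undefined.

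The risk of a chance imbalance is genuine, but it concerns how much evidence the DSMB would require. The documents tie the criterion to no particular split of deaths, so the frequency of any chosen split says nothing about the rule in force. Correcting the label would leave that risk as it is.

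Recasting mortality as a safety outcome would go further than the text supports. Section 7.3 refers to efficacy as well as safety, and section 8 speaks of superiority, so the rewording would settle a question of intent that belongs to the sponsor and the DSMB.

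**Conclusion.** The label in section 8 conflicts with the Précis and with sections 3, 4.2.1 and 4.2.2. It is a clerical slip confined to one phrase. The outcome is named explicitly, the trial's primary endpoint cannot be substituted for it, and removing the label would alter no monitoring decision, analysis, sample size or conclusion. The numerical effect is nil. What remains open, the strength of evidence the DSMB would require, is detail that a DSMB and its charter can reasonably supply.

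This rests on two readings: that section 8 means the mortality it names, and that the charter of section 7.3 is in place before results by arm are reviewed. The second cannot be verified from the documents. No change to the plan is called for.

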9 STATISTICAL CONSIDERATIONS

9.1 STATISTICAL AND ANALYTICAL PLANS

Randomized Aim

Descriptive patient characteristics will be presented as mean (SD) for continuous variables and n (%) for categorical variables. Baseline comparisons of patients assigned to CRT-P vs. CRT-D will be performed using t-tests for continuous variables (Wilcoxon rank-sum test if non-normally distributed) and chi-squared tests for categorical variables (Fisher’s Exact Test in case of small sample sizes within cells) to confirm that the randomized treatment arms are balanced in key demographics and potential confounders. The proportion of patients experiencing major/minor procedural complications within 30 days will be reported as n (%) within each treatment arm. These complication rates will be ascertained through review of pertinent medical records following the device implantation. Mortality [as n (%)] and the 6-month QOL outcomes [as mean (SD)] within each treatment arm will be reported as well. Cost of care for the index hospitalization for CRT device implantation and for the follow-up period will be measured at the conclusion of the study and compared between the 2 cohorts using a 2-sample t-test (or Wilcoxon test if the data are non-normally distributed). Retention will be presented as n (%) completing at least 6-month of follow-up. In addition to the retention, in order to document the recruitment success, we will report the number of patients approached in order to successfully enroll n=50 patients, which will be useful information in planning a large scale trial.

Observational Aim

All patients who do not enroll in the trial, but consent to be followed, will be enrolled in a parallel observational cohort. Patients’ clinical and demographic characteristics will be examined and compared between CRT-P and CRT-D recipients using t-tests, Wilcoxon rank-sum tests, chi-squared tests, or Fisher’s Exact tests, as appropriate. Patient satisfaction among CRT-P vs. CRT-D recipients will be assessed at baseline and 6 months after enrollment using the Satisfaction with Decision Scale. The scores will be presented as mean (SD) and tested using a 2-sample t-test (or Wilcoxon test if the data are non-normally distributed). Deceased patients will be included in the analysis (assigned the lowest possible satisfaction score of 6) to avoid survival bias in the event of differential mortality in CRT-P vs. CRT-D. Cost of care will also be presented as mean (SD) and compared between the two cohorts using a 2-sample t-test (or Wilcoxon test if the data are non-normally distributed). Multivariate modeling with adjustment for selected patient factors will be considered if there are differences in CRT-P vs. CRT-D patients on key demographics, but the power to test this difference while accounting for multiple confounders may be limited.

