5.4 STRATEGIES FOR RECRUITMENT AND RETENTION

Patients presenting to the outpatient cardiology clinics or inpatient services of the 4 participating institutions and who are prescribed CRT device implantation or CRT-D device change-out for battery depletion will be considered for participation in this pilot randomized trial. The main investigator at each site will identify prospective patients who may require CRT device implantation. This will be achieved by screening the inpatient services and outpatient clinics of the cardiac electrophysiology services at each site. Research coordinators will verify that the prospective subjects meet all the inclusion and none of the exclusion criteria for the study. Once this information is ascertained, the investigator, research coordinator, or both will approach the patient to explain the rationale of the study and its requirements. After signing written informed consent, patients will be randomized to receive a CRT-P or a CRT-D device. Block randomization by enrolling site will be adopted. The randomization status of the patient will be communicated to the treating cardiologist. Of note, the surgical procedure for CRT-P or CRT-D implantation is similar with respect to duration and risk of the procedure, with the exception that CRT-D implantations require a larger skin incision (~1.5 inches versus 0.75 inches).

The research coordinator at each site will maintain a log of all patients who were screened for this pilot trial. The log should include reasons for why the patient did not meet either the inclusion or the exclusion criteria. Additionally, the log would also include the patient's reason for not wanting to enroll in the Aim 1 clinical trial. This log will be maintained at each individual site and redacted of identifiable information in order to send to the sponsor upon request. Use of patient initials and age will be used in place of patient's full name and date of birth.

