6 STUDY PROCEDURES AND SCHEDULE

Randomization Aim

Table 1 details the baseline data collected for every enrolled patient. Baseline demographics (e.g. age, gender, and race) and clinical information (e.g. cardiac condition, comorbid conditions, echocardiographic parameters, EKG parameters) will be abstracted from the electronic medical records of each participating institution. QOL questionnaires will be obtained at enrollment and at the 6-month follow-up visit using both the RAND-36 health Status Inventory³⁵ and the Minnesota Living with Heart Failure Questionnaire³⁶. A paper and pencil option will be provided unless the patient is unable to read or write in which case the questionnaires will be administered verbally by a research coordinator.

Patients will be followed in the pilot randomized trial from the date of enrollment until study closure. During follow-up, information will be collected on procedural details and complications, as well as clinical events including death, hospitalizations, and emergency room visits. The events will be ascertained by asking the patient or their caregiver. Data pertaining to hospitalizations and emergency room visits will be readily available if they occurred at the enrolling institution. If at another institution, these data will be collected by asking the patient to sign a release of medical records form and by obtaining relevant clinical information from the other institution. The cause of death and primary reason for hospitalization will be adjudicated as cardiac (arrhythmic or non-arrhythmic) or non-cardiac by an adjudication committee that is independent from the research team. For the CRT-D arm of the study, information about appropriate and inappropriate device shocks and anti-tachycardia pacing therapies will be collected. Importantly, rates of patient screening, enrollment, randomization, and retention in the study will also be collected.

Table 1. Baseline Data	Variables Collected
Demographic variables	Age, Gender, Ethnic background, type of insurance (primary and secondary), Zip code

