9.2 SAMPLE SIZE

Randomized Aim

It will be of interest to estimate the recruitment success rate and the retention rate in this population, as that will be useful knowledge for designing a pivotal non-inferiority trial. The proposed sample size of 50 patients guarantees a maximum sample standard deviation = $\sqrt{(.5*(1-.5)/50)} = 7\%$, meaning that a 95% confidence interval will have a maximum margin of error $\pm 13\%$ in estimating true retention rate. However, this margin-of-error may be lower (the further the sample retention is from 50%). For example, if 40/50=80% participants enrolled complete at least the 6-month visit, a 95% CI estimating the true 6-month retention in this population would range from 68.9-91.1%, information that can be used to guide recruitment estimates for the large scale trial. The recruitment success rate can be estimated with even more precision, as there will be a larger N approached than N enrolled (and thus a smaller standard deviation of the sample proportion).

Observational Aim

It is anticipated based on the physician and patient surveys that approximately 40% of patients offered the opportunity to enroll in the pilot randomized controlled trial of Aim 1 will do so. Therefore, 125 patients will need to be screened to enroll 50 in the pilot randomized trial. It is assumed that 80% of those who decline participation in Aim 1 will agree to be followed in the observational cohort, the cohort will consist of 60 non-randomized patients. A comparison will be scored on the Satisfaction with Decision Scale using a t-test (or Wilcoxon rank-sum test, if non-normally distributed). Assuming roughly equal numbers select CRT-D vs. CRT-P, enrollment of 60 cohort participants will have 80% power to detect a difference in Satisfaction with Decision scores if one treatment group's average score is at least 0.75 standard deviations higher than the other group.

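### Section 9.1 uses baseline significance tests to confirm that the randomized arms are balanced, a conclusion those tests cannot give; the consequence is minor and the repair is nearly free

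*Combined protocol and SAP*

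**What the plan says.** All references are to the combined protocol and SAP.

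- **Section 9.1, Randomized Aim.** "Baseline comparisons of patients assigned to CRT-P vs. CRT-D" "will be performed using t-tests for continuous variables (Wilcoxon rank-sum test if non-normally distributed"), with "chi-squared tests for categorical variables" or Fisher's exact test where cells are small. The stated purpose is "to confirm that the randomized treatment arms are balanced in key demographics and potential confounders". No significance level, imbalance threshold, list of variables or action on a significant result is given. The same paragraph already plans mean (SD) and n (%) for patient characteristics.
- **Section 9.1, outcomes in the same paragraph.** Complications, mortality and 6-month QOL are reported within each arm, with no between-arm test. Cost of care is compared by a two-sample t-test or Wilcoxon test. The text there speaks of two cohorts, which I read as the two randomized arms.
- **Section 9.1, Observational Aim.** Covariate adjustment prompted by group differences is mentioned here only.
- **Section 5.4.** "Block randomization by enrolling site will be adopted". No allocation ratio is stated.
- **Section 9.2.** The 50 patients are justified by the precision of the retention and recruitment rates, not by any comparison of arms.
- **Section 6.** "Table 1 details the baseline data collected for every enrolled patient". Table 1 includes the QOL questionnaires. Table 2 has one mark for economic data, at End of Study.

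**The concern.** The plan announces a conclusion, balance, and names a significance test as the means of reaching it. The test does not bear on that conclusion in either direction.

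If patients are properly randomized, any baseline difference between the arms arose by chance. The null hypothesis of the test is then true by design. A large p-value says only that the observed difference is not unusual for chance allocation; it does not say that the difference is small. A small p-value marks one of the chance differences that must turn up when several variables are tested.

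What matters for reading outcomes is how large the realized difference is and how strongly the variable predicts the outcome. The p-value measures neither. With about 25 patients per arm, differences large enough to interest a clinical reader will often be non-significant, and the report would carry a statement of balance that the data do not support.

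**Working it through.** **Inputs.** Total N is 50 (section 9.2). I assume 25 per arm, because section 5.4 gives no ratio, and a two-sided 5% level, because section 9.1 gives none and section 9.2 uses 95% intervals. The number of variables tested is not stated; 20 is an assumption.

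**Step 1. The plan's nearest own figure.** The plan gives no power or precision for the baseline tests. For the same kind of test, section 9.2 (Observational Aim) states 80% power for 0.75 SD with 60 patients in roughly equal groups. A two-sided 5% t-test with 30 per group and a difference of 0.75 SD has 81.5% power, so that figure reproduces and the method agrees with the plan's.

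**Step 2. The largest observed difference that passes, continuous variable.** The t statistic is d / √(1/n₁ + 1/n₂), where d is the observed difference in SD units. It is non-significant while d < t(0.975; 48) × √(1/n₁ + 1/n₂), with t(0.975; 48) = 2.011.

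| Split | √(1/n₁ + 1/n₂) | Largest d with p>0.05 |
|---|---|---|
| 25/25 | √(2/25) = 0.283 | 0.57 SD |
| 20/30 | 0.289 | 0.58 SD |
| 17/33 | 0.299 | 0.60 SD |

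The unstated ratio hardly matters.

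**Step 3. Binary variable, 25 per arm.** For 10/25 against 16/25 the pooled proportion is 26/50 = 0.52 and the standard error is √(0.52 × 0.48 × 2/25) = 0.141. Then z = 0.24/0.141 = 1.70 and p is about 0.09. A gap of 24 percentage points passes. Starting from 10/25, the other arm must reach 17/25 (chi-squared) or 18/25 (Fisher) to be flagged. For a rare condition, even 5/25 against 0/25 gives Fisher p = 0.0502, so a condition with five or fewer cases in all can never be flagged.

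**Step 4. How often this happens under correct randomization.** By the normal approximation, the observed d for one continuous variable has mean 0 and standard deviation √(2/25) = 0.283. The chance that it exceeds 0.25 SD in either direction is 2 × [1 − Φ(0.25/0.283)] = 38%. About 33% exceed 0.25 SD and are still non-significant. The 0.25 SD mark is only illustrative; the plan sets none.

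**Step 5. Chance flags.** With 20 independent tests at 5%, the expected number of significant results is 20 × 0.05 = 1.0, and the chance of at least one is 1 − 0.95²⁰ = 64%. Correlation between variables lowers the chance of at least one but not the expected number; Fisher's test, being conservative, lowers both.

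**Step 6. What depends on the tests.** Within section 9.1, nothing in Aim 1 is conditional on them. The cost test is unadjusted whatever the baseline table shows, and the other clinical outcomes are descriptive.

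**The case against.** The strongest reply is that this is a customary table in a feasibility pilot and that nothing hangs on it. The second half of that is right. The primary endpoint is feasibility, N was chosen for precision of rates, and cost is the only outcome tested between the randomized arms. That limits the weight of the point. Custom does not make the stated inference valid.

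It can also be said that in an unblinded trial with blocks within site, baseline tests may signal a corrupted allocation process. That is a legitimate use, so it would be too much to say that the p-values could never inform anything. The plan does not claim that use, however; it claims balance.

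Three stronger readings are tempting, and the documents do not support them.

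- *A reader might infer that cost and QOL will be interpreted unadjusted because the check was passed.* Section 9.1 sets no such rule, and plans no QOL contrast between the randomized arms at all.
- *A reader might compute that 80% power at 25 per arm requires 0.81 SD, and infer that an imbalance of that size would pass.* That is power against a true difference, which randomization excludes. An observed 0.81 SD gives t = 0.81/0.283 = 2.86, p about 0.006, and would be flagged. The relevant limit is 0.57 SD. Nor is the fault mainly one of sample size, since more patients would not make these tests evidence of balance.
- *A reader might count every item in Table 1 and infer a near-certain false flag.* Section 9.1 restricts testing to key demographics and potential confounders, and several Table 1 conditions may be too rare to reach significance.

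**Conclusion.** Wrong as written, on the conclusion of balance. The tests planned for Aim 1 cannot confirm it: with 25 per arm and a two-sided 5% level, both assumed, differences up to about 0.57 SD or 24 percentage points (10/25 against 16/25) would pass. About one chance flag is expected per 20 tests, the number of tests being assumed. The result is insensitive to the allocation ratio.

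The consequence is minor. It affects a sentence in the report and the reading of the baseline table, not the feasibility results or any planned Aim 1 analysis. The point does not extend to Aim 2, where patients choose their device and a comparison of recipients addresses a real question.

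Adjusting the cost comparison for site is a free improvement rather than the correction of an error.

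**What to change.** In section 9.1, Randomized Aim:

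1. Delete the baseline significance tests and the statement that they confirm balance. Keep mean (SD) and n (%) by arm, and add standardized differences if wanted.
2. Adjust the cost comparison for enrolling site, prespecified and whatever imbalance is observed: a linear model with arm and site, or a site-stratified Wilcoxon (van Elteren) test if the data are non-normal. With four sites the linear model uses three further degrees of freedom (48 to 45). Adjustment for a baseline cost is not possible, since economic data are scheduled only at the end of the study.
3. No QOL contrast between the randomized arms is planned. If the sponsor chooses to make one at 6 months, adjust it for the baseline score, which is already collected.

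Leave the Aim 2 comparisons as they are. The cost is a change of wording and one added factor in one analysis. No new data, patients or visits are needed.
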